4.0	Jan 4, 2017	
 • Study Design: Clarified enrollment targets - removed numbers not accounting for attrition. • Sample Size Justification: clarified rate being tested; defined C_{DEVICE}; removed ‘exact’ specification on CI as final endpoint test will be the random effects model. • Analysis Populations: clarified primary analysis will be on ITT using multiple imputation; expanded PP definition to include removal for major deviation; clarified missing data imputation and additional sensitivity analysis to be defined in another segment. • Efficacy Endpoint Analysis: removed “low number of multi-lesion subject” section as the study had >10 subjects with multiple lesions. • Supportive Endpoint Analyses: clarified wording on “weighted average response”. • Handling of missing data: added specific imputations for primary hypothesis test; added specific imputation methods for sensitivity analyses. • Subset Analyses: Added additional subgroups of interest • Poolability Analyses: Corrected population to ITT as this is the primary endpoint population; Added a test of pooling by geography (US/OUS); changed pooling significance level to 0.05 (instead of .15 usually done to account for interactions) as this is a one group study and only main effects will be tested. • Added more specific methods of analysis throughout.

Approvals

Name	Study Role	Signature	Date
[REDACTED]	Galil – [REDACTED]	DocuSigned by: [REDACTED]	04-Jan-2017
[REDACTED]	Galil – [REDACTED]	DocuSigned by: [REDACTED]	05-Jan-2017
[REDACTED]	NAMSA – [REDACTED]	DocuSigned by: [REDACTED]	05-Jan-2017
[REDACTED]	BTG – [REDACTED]	DocuSigned by: [REDACTED]	05-Jan-2017

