5. STUDY DESIGN

This is a Phase II multicenter, prospective, single arm study. Target inclusion for this study is 226 tumors. It is estimated this study will enroll 150 patients across approximately 15 study sites in the United States and internationally in order to achieve the target tumor goal. Patients enrolled will undergo cryoablation of at least 1 metastatic pulmonary tumor via a Galil Medical cryoablation system using Galil Medical cryoablation needles.

Patients will be screened before the cryoablation procedure. After the cryoablation procedure, protocol directed follow-up visits will occur within 1 week of the cryoablation procedure and then 1, 3, 6, 12, 18, and 24 months post cryoablation procedure.

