10.1. Study Design and Sample Size Calculation

This is a prospective, single-arm study designed to determine the safety and efficacy of Galil Medical's Cryoablation System and needles in cryoablation of metastatic lung tumors.

The primary efficacy endpoint for the trial is 12-month local tumor control. The papers shown below were used as reference for clinicians who determined a clinically relevant efficacy endpoint performance goal was 84% success at 12-months.³⁶⁻⁴³ This observed cryoablation rate will be tested against this performance goal.

Paper	Tumors	12-month Local Tumor Control Success	Lower 97.5% 1-sided Wilson CI
Okuneiff (2006)	125	91%	0.8469
Rusthoven (2009)	63	100%	0.9425
Baschnagel (2013)	47	97%	0.8757
Ricardi (2012)	77	94%	0.8632
Norihisa (2008)	43	94.50%	0.8337
Yoon (2006)	101	90%	0.8261

This test is accomplished by testing against the following hypotheses:

$$H_0: C_{\text{DEVICE}} \leq 84.0\%$$

$$H_a: C_{\text{DEVICE}} > 84.0\%$$

The null hypothesis will be rejected and the primary efficacy endpoint performance goal will be met if the lower bound of the exact one-sided 97.5% confidence interval for the six-month closure rate is greater than 84.0%.

PASS 12 was used to calculate the sample size needed. A sample size of 203 tumors achieves 85% power (and guarantees at least 80% power) to detect a difference ($P_1 - P_0$) of 0.0700 using a one-sided binomial test. The target significance level is 0.0250. The actual significance level achieved by this test is 0.0239. These results assume that the population proportion under the null hypothesis is 0.8400.

Power Analysis of One Proportion

Numeric Results for testing $H_0: P = P_0$ versus $H_1: P > P_0$

Test Statistic: Exact Test

Power	N	Proportion Given H_0 (P_0)	Proportion Given H_1 (P_1)	Target Alpha	Actual Alpha	Reject H_0 Beta If $R \geq$ This
0.8501	203	0.8400	0.9100	0.0250	0.0239	0.1499 181

To account for up-to a 10% 12-month tumor attrition rate, the final sample size has been increased to 226 tumors.

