The primary efficacy endpoint for the trial is 12-month local control. The papers shown below were used as reference for clinicians who determined a clinically relevant efficacy endpoint performance goal was 84% success at 12-months. This observed cryoablation group's local control rate will be tested against this performance goal.

Paper	Lesions	12-month Local Control Success	Lower 97.5% 1-sided Wilson CI
Okuneiff (2006)	125	91%	0.8469
Rusthoven (2009)	63	100%	0.9425
Baschnagel (2013)	47	97%	0.8757
Ricardi (2012)	77	94%	0.8632
Norihisa (2008)	43	94.50%	0.8337
Yoon (2006)	101	90%	0.8261

This test is accomplished by testing against the following hypotheses:

$$H_0: C_{\text{DEVICE}} \leq 84.0\%$$

$$H_a: C_{\text{DEVICE}} > 84.0\%$$

where C_{DEVICE} is the observed cryoablation local control rate at 12-months.

The null hypothesis will be rejected and the primary efficacy endpoint performance goal will be met if the lower bound of the one-sided 97.5% confidence interval for the 12-month tumor local control rate is greater than 84.0%.

PASS 12 was used to calculate the sample size needed. A sample size of 203 lesions achieves 85% power (and guarantees at least 80% power) to detect a difference ($P_1 - P_0$) of 0.0700 using a one-sided binomial test. The target significance level is 0.0250. The actual significance level achieved by this test is 0.0239. These results assume that the population proportion under the null hypothesis is 0.8400.

Power Analysis of One Proportion

Numeric Results for testing $H_0: P = P_0$ versus $H_1: P > P_0$

Test Statistic: Exact Test

Power	N	Proportion		Target Alpha	Actual Alpha	Beta	Reject H_0 If $R \geq$ This
		Given H_0 (P_0)	Given H_1 (P_1)				
0.8501	203	0.8400	0.9100	0.0250	0.0239	0.1499	181

To account for up-to a 10% 12-month lesion attrition rate, the final sample size has been increased to 226 lesions.

Note that, for the purposes for sample size calculations, the observations are assumed to be independent. However, the primary analyses will account for within subject correlation, as described below.

General Analysis Methods

Data will be analyzed using descriptive statistics. Continuous variables (e.g., age) will be summarized by the number of patients, mean, standard deviation, median, interquartile range, minimum and maximum. Categorical variables (e.g., race) will be summarized by frequencies and percentages of patients in each category. 95% confidence intervals will be calculated as appropriate.

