Analysis Populations

All primary analyses will be performed on all tumors with a Galil Medical Cryoablation System and needles as the intent-to-treat evaluable population. A supplemental per-protocol analysis

will be done for the primary endpoint, removing tumors that 1) did not have a complete treatment; and subjects who 2) did not meet the study criteria but were enrolled; or 3) had a deviation with high likelihood of affecting the study outcome (as determined by a review of all occurring deviations).

The intent-to-treat and per-protocol analyses will be compared for level of agreement. It is expected that the two populations will be similar; however, any substantial differences between the two will be analyzed appropriately to elucidate the cause of these differences. Missing data will be imputed for the primary analysis as outlined in section "Handling of Missing Data" section later in the SAP. Additional sensitivity analyses using alternate missing data imputation will be presented.

Efficacy Endpoint Analysis

Efficacy Endpoint

The primary efficacy endpoint for this study is assessment of cryoablation on local tumor control in patients with pulmonary metastatic disease at 12 months post cryoablation.

Analysis Methods

The primary efficacy endpoint for this study is defined as follows: local tumor control in patients with pulmonary metastatic disease at 12 months post cryoablation. Tumor control will be defined by the criteria defined in Section 9.7 of this protocol.

Patients are allowed up to 6 tumors and the primary efficacy endpoint (tumor control) will be calculated on a per tumor level.

The rate of local tumor control at 12-months will be analyzed using a random effects logistic regression model accounting for within subject correlation to account for multiple tumors per subject. The null hypothesis will be tested comparing the lower bound of the Wald 97.5% one-sided confidence interval for the estimated rate of local tumor control to the performance goal of 84.0%. If the lower bound is greater than 84.0%, the null hypothesis will be rejected and the endpoint will be considered met.

Safety Endpoint Analysis

Safety Endpoint

The safety endpoint for this study is to assess the incidence and severity of cryoablation related adverse events.

Analysis Methods

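### The 85% power and the guaranteed 80% belong to an exact test on 203 independent tumours, not to the clustered random-effects Wald test that decides the primary endpoint

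*SAP*

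**What the plan says.** The SAP (Sample Size Justification) reports "A sample size of 203 lesions achieves 85% power (and guarantees at least 80% power) to detect a difference" of 0.07 above the 84% performance goal. Its power table is headed "Test Statistic: Exact Test" and rejects at 181 or more controlled tumours out of 203. The section then adds that "for the purposes for sample size calculations, the observations are assumed to be independent", and that the primary analyses will nevertheless account for correlation within subjects. The increase from 203 to 226 is attributed to 10% attrition.

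Under Efficacy Endpoint Analysis, Analysis Methods, the 12-month rate is to be "analyzed using a random effects logistic regression model accounting for within subject correlation", and the decision rests on the "lower bound of the Wald 97.5% one-sided confidence interval for the estimated rate of local tumor control". The revision history confirms the intent: the exact wording was taken out as a "specification on CI as final endpoint test will be the random effects model".

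Protocol 10.1 repeats the claim, "A sample size of 203 tumors achieves 85% power (and guarantees at least 80% power"), with no caveat about independence, and it still specifies an exact interval. On clustering, Protocol 5 says "It is estimated this study will enroll 150 patients" to reach 226 tumours, and both documents allow up to 6 tumours per patient.

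Among the supportive analyses, the SAP defines a weighted average response: patient-level response weighted by the number of lesions evaluated, with an exact 95% interval.

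**The concern.** A power statement describes one test under one data model. Here the test was changed to a random-effects model, and the data model was acknowledged to be clustered, but the 85% and the 80% floor were carried over. If the trial misses 84%, the result will be read as a failure in a study with at least 80% power.

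The SAP also leaves open two choices that affect the power of its test. It does not say whether the estimated rate under the Wald bound is the marginal (population) rate or the conditional rate from the back-transformed intercept. It does not say how the model is fitted.

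A smaller matter is that the exact interval for the weighted average response may ignore clustering in the same way.

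**Working it through.** **Inputs from the documents.** P0 = 0.84, P1 = 0.91, one-sided alpha 0.025, N = 203, reject at R ≥ 181, 226 tumours, 150 patients, 1 to 6 tumours per patient.

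**Assumed.** The ICC (on the observed success/failure scale) and the distribution of tumours per patient, because the documents give neither.

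**1. Reproduce the printed figures.** Exact binomial, n = 203, R ≥ 181: alpha = 0.0239 and power = 0.8501, as printed. 203/0.9 = 225.6, rounded up to 226. At n = 202 exact power is 0.796. From n = 203 to 399 it never falls below 0.816. The 80% floor thus reproduces for the independent exact test.

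**2. Bound the cluster size.** The mean is 226/150 = 1.507. The quantity that drives the design effect is the size-weighted mean, m_w = E[m²]/E[m].

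- All patients with 1 or 2 tumours: 50.7% have 2, so m_w = (0.493 + 4 × 0.507)/1.507 = 1.67, the minimum.
- All patients with 1 or 6 tumours: 10.1% have 6, so m_w = (0.899 + 36 × 0.101)/1.507 = 3.02, the maximum.

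**3. Design-effect power.** DE = 1 + (m_w − 1) × ICC and n_eff = 203/DE. The normal approximation is power = Φ[(0.07√n_eff − 1.96√(0.84 × 0.16)) / √(0.91 × 0.09)].

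| ICC | DE | n_eff | Power |
|---|---|---|---|
| 0 | 1.00 | 203 | 83.5% |
| 0.1 | 1.07–1.20 | 190–169 | 81–75% |
| 0.3 | 1.20–1.61 | 169–126 | 75–59% |

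Power of 80% needs n_eff = 187.8, so DE = 203/187.8 = 1.081. The floor is lost at ICC = 0.081/0.67 = 0.12 (m_w 1.67) or 0.081/2.02 = 0.04 (m_w 3.02).

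**4. Simulate the SAP model.** Random-intercept logistic data, true marginal rate 0.91, 203 complete lesions, 3,000 replicates per cell. Three layouts: 1–2 tumours (m_w 1.67), mixed 1–6 (2.15), and 1 or 6 (3.07). Maximum likelihood used 40-point quadrature with a logit-scale Wald bound. Multiple imputation was not modelled.

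| Fit and rate under the bound | ICC 0 | ICC 0.1 | ICC 0.3 |
|---|---|---|---|
| Maximum likelihood, marginal rate | 80–83% | 73–82% | 70–75% |
| Maximum likelihood, intercept | 52–55% | 35–38% | 25–26% |
| Pseudo-likelihood, intercept | 83–86% | 81–83% | 83–84% |

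The pseudo-likelihood version keeps the floor, but its type I error is 4.2–4.5% at ICC 0.3. A separate simulation of the marginal-rate version (203 tumours in 136 patients, 1,500 runs) gave about 83 / 81 / 78 / 75% at ICC 0 / 0.04 / 0.12 / 0.24.

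**5. The protocol's exact rule under clustering.** Applying R ≥ 181 to clustered data (20,000 replicates) gives power of 80–85%. Type I error is 2.7–3.4% at ICC 0.1 and 3.7–5.9% at 0.3, against the printed 2.39%.

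**6. Weighted average response.** With r_i controlled of m_i lesions in patient i, Σ m_i(r_i/m_i)/Σ m_i = Σ r_i/Σ m_i. This is the pooled lesion proportion, so an exact interval treats lesions as independent. Coverage of the nominal 95% interval (beta-binomial, 40,000 replicates) is 94–96% at ICC 0.1 and 90–94% at 0.3, with 90% only in the 1-or-6 layout.

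**The case against.** The printed arithmetic is right, and the SAP is open about it: it names the binomial test, heads the table as exact and states the independence assumption. That stands. The gap is an uncorrected claim, not a hidden one. But disclosing independence does not support a guarantee in the same section when the next sentence says the analysis will not assume it.

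The revision history refers only to the interval, so its difference from the power table is not in itself an error. Agreed. It is used here only as evidence of which test is final.

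The protocol's own rule is exact, and under clustering its power stays at about 80–85%. This also stands: what that rule loses is mainly type I error control. The protocol claim still needs qualifying, because it carries no independence caveat and the SAP decides the endpoint by another test.

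The figures use 203 complete lesions, the full 10% attrition. With 226 complete lesions the same approximation gives 87.8% at ICC 0, and the floor is lost at ICC 0.10–0.30 (226/187.8 = 1.203; 0.203/2.02 and 0.203/0.67). The loss may therefore be smaller, but the plan's own statement is for 203. Also, 1.5 points of the gap from 85.0% to 83.5% come from the normal approximation alone.

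The SAP defines the tested rate as an observed rate, which favours the marginal reading. That is the more natural reading, so the intercept results under maximum likelihood should not be taken as the expected power. They show why the choice must be written down. The 1-or-6 layout is an extreme bound, and the supportive interval is a minor matter.

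**Conclusion.** The concern holds. The 85% and the 80% floor are correct for 203 independent tumours and R ≥ 181. They are not the power of the random-effects Wald test, for which the plan gives no figure.

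The size of the loss cannot be fixed from the documents. On the marginal reading with maximum likelihood, 203 complete tumours give roughly 73–82% power at ICC 0.1 and 70–75% at ICC 0.3. At low ICC with mostly one or two tumours per patient, the loss is a few points. The unspecified rate and fitting method can move power by tens of points. These results rest on assumed ICCs and layouts and leave out imputation. That the power figure and the planned test do not match needs no such assumption. Under-coverage of the supportive interval is small to modest.

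**What to change.** - In both documents, remove the guarantee and label 85% as the power of the exact test with independent tumours.
- In the SAP, state whether the Wald bound is for the marginal or the conditional rate, and name the fitting method.
- Report power simulated under exactly that model and bound, over a range of ICCs and tumours-per-patient distributions, with type I error alongside. The figures above are illustrations and should not be inserted as the power of the SAP test.
- Replace the exact interval for the weighted average response with a cluster-robust or patient-level bootstrap interval.

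The cost is wording in two documents and one simulation. No patients are added and the 84% goal is unchanged. The stated power will probably look less favourable, and one supportive interval will be slightly wider.

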10.3. Analysis Populations

All primary efficacy analyses will be performed on all treated tumors with a Galil Medical Cryoablation System and needles as intent-to-treat population. A supplemental per-protocol analysis will be done for the primary efficacy endpoint, removing index tumor which did not have a complete treatment and/or those that did not meet the study criteria but were enrolled.

The intent-to-treat and per-protocol analyses will be compared for level of agreement. It is expected that the two tumor populations will be similar; however, any substantial differences between the two will be analyzed appropriately to elucidate the cause of these differences.

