Demographics, disease status, imaging data, lung function, and protocol deviations will be summarized using descriptive statistics. These measures include but may not be limited to:

Demographics

- Age at the date of consent
- Sex
- Race and ethnicity (Per French regulations, race and ethnicity will not be collected at any study site in France.)
- Height, weight, and BMI
- Comorbidities
- Smoking history
- Concomitant medications

Disease status

- Primary cancer diagnosis
- Prior treatment(s) for lung metastases
- Lung or other metastatic disease
- Baseline laboratory data

Index Tumor(s)

- Histology of primary tumor
- Proof of metastases
- Location of the index tumor(s) in the lung(s)
- Size of the index tumor(s)
- Number of index tumors
- Number of new tumors

Procedure/Discharge

- Number of tumors treated with cryoablation
- Index tumor size measurement:
 - 3 axes of measurements (cm) and
- Number and type of cryoablation needles used
- Freeze and thaw times, per cycle
- Number and type of intra-operative complication(s)
- Severity of complication(s)
- Requirement for hospital admittance/stay
- Requirement for surgical intervention(s)

All protocol deviations

Study Completion/Withdrawals

Subject Disposition

Subject disposition will be presented as:

- Number of subjects enrolled

- Number of subjects completing each follow-up visit
- Number of subjects withdrawn or lost to follow-up
- Number of subject deaths
- Number of subjects evaluable for ITT and PP analyses

Randomization and Blinding

As this is a single arm study, no randomization or blinding will be performed. To minimize selection bias within the enrolled patient population, participation in the study is to be offered to all eligible patients on a consecutive basis as they present to the physician at the site.

Handling of Missing Data

Missing data will be prospectively minimized through training of the participating investigator and site staff, and through appropriate clinical trial management. Every effort will be made to collect all data points in the study. All patient data that is available on patients who drop out during the course of the study will be included where possible. Sensitivity analyses will be conducted to determine the effect of missing data on the primary efficacy endpoint.

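### The SAP's per-protocol set removes whole subjects where the protocol removes tumors, and its added deviation exclusion is a judgment with no masking or date

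*SAP*

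**What the plan says.** Protocol section 10.3 defines the per-protocol set by "removing index tumor which did not have a complete treatment and/or those that did not meet the study criteria but were enrolled". It contains no exclusion for protocol deviations.

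The SAP (Analysis Populations) starts by "removing tumors that 1) did not have a complete treatment; and subjects who 2) did not meet the study criteria but were enrolled". It then adds a third ground, also attached to subjects: those who "had a deviation with high likelihood of affecting the study outcome (as determined by a review of all occurring deviations". The SAP revision history records this addition in the entry dated January 4, 2017: "expanded PP definition to include removal for major deviation".

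The role of this set is limited. The SAP calls it "A supplemental per-protocol analysis", and states that "All primary analyses will be performed on all tumors with a Galil Medical Cryoablation System and needles as the intent-to-treat evaluable population". Its use is as a check: "The intent-to-treat and per-protocol analyses will be compared for level of agreement". Neither document gives a measure or threshold for agreement. Both say that substantial differences will be examined for their cause.

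**The concern.** There are two separate problems.

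**Unit of exclusion.** The primary endpoint is scored per tumor and a patient may contribute up to six. Protocol sections 6.2.5 and 6.2.6 (maximum size of 3.5 cm, accessible location) describe individual tumors. Under the SAP, a patient with one tumor that breaches either criterion loses every tumor from the per-protocol set. Under the protocol, only that tumor goes. Two analysts following the two documents would build different data sets.

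**Discretion.** The deviation ground is itself a judgment about influence on the outcome. The SAP lists no qualifying deviations, names no reviewer, sets no date relative to the primary analysis, and does not say that follow-up imaging results are kept from whoever decides. The SAP also states that "As this is a single arm study, no randomization or blinding will be performed", and protocol section 16.2 has site investigators read the post-ablation images alongside the central review. Outcome information therefore accumulates while deviations do.

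What is at stake is whether the comparison of intent-to-treat and per-protocol results says anything. If membership of the second set can depend on results, neither agreement nor disagreement can be taken at face value.

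**Working it through.** **1. The rules side by side**

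| Ground for removal | Protocol 10.3 | SAP |
|---|---|---|
| Incomplete treatment | tumor | tumor |
| Study criteria not met | index tumor (natural reading) | subject |
| Deviation judged likely to matter | none | subject |

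The conflict is confined to the second row. The third row is an addition without a protocol counterpart.

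**2. The plan's own figures.** With N = 203, null rate 0.84, alternative 0.91 and rejection at 181 or more, exact binomial tails give alpha 0.0239 and power 0.8501, as stated. Attrition: 203 / 0.9 = 225.6, so 226. Planned tumors per patient: 226 / 150 = 1.51.

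**3. Effect of the unit.** For a patient with m tumors, one of them ineligible, the protocol removes 1 and the SAP removes m. Eligible tumors lost: m − 1, at most 5.

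The counts below are assumed. Start from 178 controlled of 203. Five patients each have one ineligible tumor that failed, and their other tumors are controlled. Tumor-level removal leaves 178 / (203 − 5). Subject-level removal leaves (178 − 5(m − 1)) / (203 − 5m). The lower bound is the exact one-sided 97.5% limit, the 0.025 quantile of Beta(x, n − x + 1).

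| Rule | Result | Rate | Lower bound |
|---|---|---|---|
| No removal | 178/203 | 87.7% | 0.824 |
| Tumor only | 178/198 | 89.9% | 0.848 |
| Subject, m = 2 | 173/193 | 89.6% | 0.8445 |
| Subject, m = 3 | 168/188 | 89.4% | 0.8405 |
| Subject, m = 6 | 153/173 | 88.4% | 0.827 |

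The unit matters little near 1.5 tumors per patient and more for patients with many tumors. In this example the subject-level rule works against the device.

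**4. Effect of discretion.** Same bound, assumed counts:

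- 180/203: bound 0.835, below 0.84. Remove two failed tumors: 180/201, bound 0.845, above.
- 181/203: bound 0.8405, above. Remove two controlled tumors: 179/201, bound 0.839, below.
- 185/203 (91.1%): remove five. If all failed, 185/198 = 93.4%, bound 0.890. If all were controlled, 180/198 = 90.9%, bound 0.860. Both stay above the goal.

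A handful of exclusions matters only when the result lies close to 84%.

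**5. Limit of the illustration.** The exact bound treats tumors as independent. The SAP uses a Wald bound from a random-effects logistic model, which cannot be computed without patient-level data. The crossing point depends on the method: a simple Wald bound on the proportion for 180/203, ignoring clustering, is 0.8867 − 1.96 × √(0.8867 × 0.1133 / 203) = 0.8867 − 0.0436 = 0.843, already above 0.84. The figures show the scale of movement, not where the SAP's test would change.

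**The case against.** A reader might infer that exclusions are made with outcomes known, so that agreement with the intent-to-treat result can be produced at will, to the device's advantage. The documents do not support that. The SAP describes a review of deviations, not of results, and nowhere says that 12-month status is available to the reviewers. The statement about blinding appears in the section on randomization and concerns treatment allocation. The revision-history entry that added the criterion shows that the number of multi-lesion subjects was known by then, but not that outcomes were. What remains is that the SAP does not rule such knowledge out. Nor is the direction fixed: step 4 moves both ways, and the subject-level unit can lower the rate.

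The consequence is also contained. The formal test is on the intent-to-treat set with multiple imputation. Worst-case, best-case and complete-case analyses are planned, as are patient-level and weighted analyses. All deviations, and the numbers evaluable for each set, are to be reported, so exclusions would be visible in part. All of this stands and limits the weight of the point.

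On the unit, most eligibility criteria (age, KPS, platelets, INR, ANC, infection) belong to the patient, and removing the patient for these is reasonable. The protocol's wording is loose, and the reference to enrollment could be read as meaning patients. But the grammatical antecedent is the index tumor, and the next paragraph of 10.3 speaks of tumor populations. The conflict therefore stands for tumor-level criteria.

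**Conclusion.** The point holds as a minor one. As written, the SAP conflicts with protocol 10.3 on the unit of exclusion for eligibility failures, and would discard up to five eligible tumors per affected patient from a per-tumor analysis. It also adds a subject-level deviation exclusion that rests on judgment, with no safeguard against knowledge of follow-up imaging. The intent-to-treat/per-protocol comparison is weakened in either direction. The primary test and its alpha are untouched.

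In size, near the performance goal about two tumors can carry an exact per-protocol bound across 84%. At the design rate of 91%, five exclusions do not. This rests on assumed counts, on independence between tumors, and on reading the protocol's eligibility clause as referring to index tumors. How many patients would be affected cannot be known from the documents.

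**What to change.** 1. In the SAP, apply tumor-level grounds (size, location, incomplete treatment, a procedural deviation specific to one tumor) to that tumor only. Remove a subject only for patient-level criteria.
2. Make protocol 10.3 and the SAP say the same thing, including whether a deviation ground exists and what the unit is for eligibility failures.
3. Decide each deviation exclusion from the deviation log with follow-up imaging results withheld, and record it with a date before the primary analysis. A deviation that concerns imaging, such as a missed scan, can be judged from the log entry without the reading.

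The cost is wording in the SAP, a clarifying line in the protocol, and one masked listing. The deviation review is already planned. No new data are needed and the primary analysis does not change.
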